12.2.3 Outcome

The outcome of an AE is assessed by the investigator using the following definitions:

- Recovered: Fully recovered or the condition has returned to baseline
- Recovered with sequelae: As a result of the AE the subject suffered persistent disability/incapacity. If the sequelae qualify as a SAE, the AE must be reported as such
- Not recovered: The condition has not returned to baseline, however, symptoms may have improved
- Fatal: Event that results in death
- Unknown: The outcome is unknown. This term should only be used when no other definition is possible e.g. the subject is lost to follow-up

12.3 Collection, recording and reporting of AEs

At each contact with the trial site, the subject must be asked about AEs in an objective manner such as "Have you experienced any problems since the last contact?".

AEs must be recorded on the AE form. One single AE form must be used per AE from start to resolution. For SAEs, the SAE form must also be filled in.

In case of concomitant medication for treatment of the AE, the concomitant medication form must be filled in.

If the same type of AE occurs more than 1 day in a row with the same pattern and severity (e.g. itching in the mouth for 5-10 minutes after intake of IMP) it is considered a recurrent AE. The AE form should be filled in with the start date and the description. Once the AE does no longer reoccur after IMP intake, the AE form should be completed with a stop date and the event should be marked as recurrent in the eCRF. If the AE then re-appears on a subsequent day or if the AEs changes in severity, a new AE form should be filled in. For recurrent events, the investigator should ask the patient about approximate daily duration and record this in the eCRF.

The investigator should record the diagnosis, if available. If no diagnosis is available, the investigator should record each sign and symptom as individual AEs. Further, the diagnosis of the underlying disease should be reported instead of a procedure performed due to the disease (e.g. if a subject undergoes surgery due to appendicitis, appendicitis (and not the surgery performed) should be reported).

The AE start time of AEs that occur on V2 will be recorded in source documents and entered into the eCRF.

12.3.1 Solicited AEs

The diary (See Appendix 4) will be used by the subject to help remember details and dates, when discussing AEs and concomitant medication with the investigator at the visits.

The diary lists 15 specific signs/symptoms, identified as local side effects of sublingual immunotherapy (Passalacqua et al. 2013). These local side effects will be collected on a daily basis by the subject during the 28 days of treatment (section 11.16).

See Appendix 5 for preferred terms used (PT) to identify solicited AEs.

12.3.2 Eosinophilic Oesophagitis

During the trial, subjects will be monitored for emerging symptoms of eosinophilic oesophagitis at the scheduled visits as described in section 11.11.

12.3.3 Reporting of AEs

The investigator must report all SAE and ESI information (initial as well as follow-up) to ALK within 24 hours after obtaining knowledge of the information. SAEs and ESIs will automatically be sent to ALK via the eCRF system. In case the eCRF system is unavailable during the 24-hour reporting timeline, SAEs and ESIs (including relevant data e.g. demography, medical history, concomitant medication) must be reported by email to ALK. For the ESI of adrenaline/epinephrine administration, the symptoms and/or circumstances that triggered the use of adrenaline/epinephrine must be clearly recorded as AEs in the eCRF.

Non-serious AEs should be reported within 5 working days after obtaining knowledge of the information.

If requested, please forward supporting documents to ALK via email. Please state the trial ID (MT-18) and the site and subject ID on all documents.

IMPORTANT: Any information that could reveal the identity of the trial subject must be hidden or removed in the source documentation. Also, information that is not relevant for the subject and the subject's condition must be hidden or removed.

Email address: [contact]

Emergency [contact]

The assessment of listedness is performed by ALK according to the reference safety information in the current version of the approved IB.

ALK will inform the regulatory authorities and IECs in accordance with local requirements in force and the ICH guidelines for Good Clinical Practice (GCP) (ICH 1996).

12.3.4 Follow-up on AEs and SAEs

SAEs must be followed up until resolution and until all queries have been resolved. The investigator must respond to SAE follow-up requests from ALK without delay and no later than 7 days after receiving the request.

Ongoing SAEs can be closed at the FU-TC with the term “not recovered” for chronic diseases (as evaluated upon medical evaluation by the investigator or the sponsor).

The investigator must ensure that the worst-case severity and seriousness of an event is kept throughout the trial.

Non-serious AEs must be followed up until resolution or until the FU-TC.

12.3.5 Reporting of medication errors, including overdose, abuse and misuse

Medication errors, including events of overdose, abuse or misuse must be reported on an AE form within 5 calendar days of obtaining the information. Reporting of overdoses must be based on actual IMP exposure as reported by the subject and not on drug accountability procedures. For overdose cases, the descriptive terms accidental or intentional overdose should be used. If an event is classified as an SAE, it must be reported as such.

12.3.6 Reporting of significant laboratory events

All laboratory reports must be reviewed by the investigator for significance.

Significant laboratory events present at screening should be recorded in the medical history section in the eCRF.

12.3.7 Reporting of pregnancies

The investigator must report information on pregnancy and pregnancy follow-up information within 14 calendar days of obtaining the information, using the pregnancy form. For further information see section 12.6.

12.3.8 Reporting of SAE and pregnancies after last subject contact (FU-TC)

SAEs that in the opinion of the investigator are related to IMP that are brought to the attention of the investigator after the last subject contact (FU-TC) must be reported immediately by using the contact details listed in this section.

All pregnancies occurring in trial subjects while exposed to IMP that are brought to the attention of the investigator after the last subject contact (FU-TC) must be reported within 14 days by using the contact details listed in this section.

12.4 Safety surveillance

Safety surveillance will be performed by ALK at pre-specified intervals to evaluate safety data and perform ongoing evaluation of AEs and SAEs

12.5 Data monitoring committee (DMC)

In this trial there will not be a DMC as it is an open-label trial, and the product is already marketed for adolescents in Europe where the trial will be conducted.

12.6 Pregnancy

Female subjects must be advised to notify the investigator immediately if they become pregnant. If a female subject becomes pregnant, she must discontinue the trial.

The investigator must report any pregnancy reported during the trial to ALK. Subjects will be informed that the investigator will report any pregnancy during the trial to ALK and that she will be asked to provide information about her pregnancy, delivery and health of her infant until the age of one month. If deemed relevant to collect information from the male partner, a separate informed consent has to be obtained.

Complications in relation to pregnancy must be reported as AEs. In case of spontaneous abortion, any malformation of the foetus, foetal death, stillbirth or a congenital anomaly/birth defect/developmental delay, the event must be reported and followed up as an SAE.

Any abnormalities observed in a child (up to 2 years of age) and suspected to be related to intra-uterine exposure to the IMP should be reported to ALK.

13 EARLY TERMINATION OF TRIAL

ALK reserves the right to terminate the trial due to safety concerns.

If the trial is prematurely terminated or suspended, the investigator should promptly inform the subjects/legal representatives and ensure appropriate therapy and follow-up. Furthermore, the investigator and/or ALK should promptly inform the IEC and provide a detailed written explanation. The regulatory authorities should be informed according to national regulations.

Early trial termination may be the result of any single criteria specified below:

1. IMP-related death of an individual
2. IMP-related anaphylactic shock in at least 2 subjects³³ defined as:

Acute onset of an illness (minutes to several hours) with involvement of the skin, mucosal tissue, or both (e.g., generalised hives, pruritus, or flushing, swollen lips, tongue, or uvula) AND medically confirmed reduced BP with associated symptoms of end-organ dysfunction (e.g., hypotonia [collapse], syncope, incontinence).

Low systolic BP for children is defined as less than $70 \text{ mmHg} + (2 \times \text{age})$ from 1 to 10 years, and less than 90 mmHg for 11 to 17 years of age.

IMP intake may only be resumed after the information has been presented to regulatory authorities, and regulatory authorities concur with continued IMP intake. In case of complete premature IMP discontinuation, participating investigators/subjects/legal representative, the IEC, and the relevant regulatory authorities will be promptly informed.

³³ The criterion for 2 events is based on prior trial experience where it has been observed that events of severe anaphylactic reactions unrelated to IMP may occur in allergic subjects even with a temporal relationship to tablet administration.

14 DATA HANDLING

An eCRF will be used for this trial. The data is entered by trained site investigator/staff into the eCRF according to guidelines. A completed eCRF is required for each subject who signs an informed consent. All eCRFs must be completed in English.

The completed eCRFs are the property of ALK and must not be made available in any form to third parties (except for authorised representatives of appropriate governmental health or regulatory authorities) without written permission of ALK.

14.1 eCRF

Data generated by the trial site and relevant for the trial will be recorded in the eCRF.

The sponsor or its representative will supply sites with access to the eCRF. The sponsor will train the site staff in the use of the eCRF. There will be no access to the eCRF without documented training in the system.

All eCRF data must be verified and approved by an investigator at the site.

The Clinical research associate (CRA) will review the eCRF for completeness and accuracy and instruct the personnel at the trial site to make any required corrections or additions according to an eCRF completion guideline.

The information entered into the database is systematically checked and errors or omissions will result in queries, which will appear in the eCRF for resolution. Concomitant medications entered into the database will be coded using the World Health Organisation Drug Reference List (WHO Drug, version WHO DDE C3 March 1, 2017 or higher).

Medical history and AEs will be coded using Medical Dictionary for Regulatory Activities (MedDRA) (version 22.1 or higher).

The writing access to the eCRF will be revoked for all site staff prior to database lock, but the reading access will not be revoked until the investigator have received all subject PDF files.

14.2 Query handling

Query handling at the trial site will be performed according to the guidelines for the eCRF system. Queries are created by programmed validation checks according to an edit check specification. Queries will also be created based on manual data checks.

All data changes/query decisions are created with an audit trail capturing the old information, the new information, identification of the user making the correction, the date the correction was made, and the reason for change.

14.3 Laboratory data

Laboratory samples will be processed at a central laboratory selected by ALK. When the samples have been analysed and the data released, a laboratory report will be e-mailed to the investigator. The investigator must review and sign the laboratory reports. The lab data will also be transferred electronically to the eCRF for investigator evaluation of outliers. At the end of trial, the laboratory data will be provided electronically to data management at ALK.

14.4 Database lock

When the database has been declared to be complete and accurate, the database will be locked. All accesses to the eCRF will be set as "read only". CRAs and non-sponsor staffs "read only" accesses will be revoked from the eCRF, when PDF files are received at site.

If changes to trial data become necessary after database lock, this must be performed according to the current ALK SOP.

A data archive for the site subject data files are produced and sent to the site.

The investigators must sign and date the data archive approval form and send it back to the sponsor.

15 STATISTICAL METHODS

Statistical analyses will be carried out by ALK. All computation will be performed using the statistical analysis system (SAS), SAS® version 9.4 or later.

Any changes in the statistical methods compared to what is described in the protocol will be documented in the ICTR. Post-hoc analyses, if any, will be clearly marked.

Summary tables for numerical variables will display the descriptive statistics mean, SD, median, 5%-quantile, 25%-quantile, 75%-quantile, 95%-quantile, minimum and maximum.

Summary tables for categorical variables will be frequency tables displaying numbers and percentages.

15.1 Sample size and power considerations

Approximately 250 subjects will be included in the study.

The study will supplement the safety database supporting an application for extension of the indication into the adolescent population in markets where the HDM SLIT-tablet is currently only approved for use in adults. Therefore, the number of subjects has been chosen so that in total, at the time of submission, approximately 500 adolescent subjects have been exposed to the HDM SLIT-tablet (12 SQ-HDM dose) in clinical trials.

The rationale for doing this, is to be able to exclude a 1% or higher proportion of subjects experiencing an AE for rare events, when the observed proportion is 0.2%. The argumentation is as follows: no events of severe systemic allergic reactions or severe local swellings have been reported in the 265 adolescent subjects exposed to 12 SQ-HDM in clinical trials, indicating that the risk in adolescents is no higher than that observed in adults. If 1 event were to occur in this study, it will correspond to an overall proportion of 0.2%, and the upper limit of the two-sided 90% confidence interval for the proportion will then be 0.95%, i.e. it can be concluded that the true proportion with 90% confidence will be lower than 0.95%, or in other words a true proportion of 1% is excluded with 90% confidence.

15.2 Analysis data sets

The total analysis set comprises all subjects who entered the trial. This analysis set includes screening failures. The total population will be used for listing reasons for screening failures and AEs before enrolment.

The safety analysis set is all subject who received at least one dose of IMP. The safety analysis set will be used for all tables and listings.

15.3 Subject disposition

A table of subject disposition displaying number and percentage of subjects screened, enrolled, included in the safety analysis set, discontinued and the primary reason for discontinuation will be presented.

15.4 Baseline characteristics

Demographic variables (including age, sex, race, ethnic origin, country/region, weight, height, and body mass index [BMI]) will be summarised.

Baseline characteristics (including baseline asthma status, inhaled corticosteroid use, duration of HDM AR/C, and HDM wheal size from SPT), primary and secondary diagnoses, and prior and concomitant therapies will be summarised.

15.5 Extent of exposure

The duration of treatment for each subject will be evaluated by calculating the number of days on IMP treatment. The range and mean for days on IMP treatment will be calculated for the safety analysis set population

For each subject, percent compliance with IMP will be calculated using the following formula:

$$\text{Percent compliance} = \frac{\text{number of days on IMP treatment}}{\text{number of expected days on IMP treatment}} \times 100\%$$

A day within the trial will be considered an "on IMP treatment" day, if the subject takes the required medication as instructed. When a subject takes less than or more than the required medication on a day, that day is not considered an "on IMP treatment" day.

For subjects who are followed for the entire trial period, the "Number of expected days on IMP treatment" is the number of days from the first scheduled treatment day to the last scheduled treatment day. For subjects who discontinue from the trial, the "Number of expected days on IMP treatment" is the number of days from the first scheduled treatment day to the last dose day.

Exposure, defined as number of expected days on IMP treatment, and percent compliance will be summarised.

15.6 Medical history

Medical history will be summarised.

15.7 Concomitant therapy

Concomitant medication and illness will be summarised.

15.8 Safety analyses

The evaluation of safety results will be based on TEAEs. TEAEs are defined as adverse events with start date on or after the time of first IMP administration and no later than 7 days after last IMP administration.

No statistical hypothesis testing will be performed.

All adverse events occurring in the trial including non-TEAEs will be listed.

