1.4 benefit-risk assessment	A section including COVID-19 related risk in context of this trial is inserted	According to latest guidelines, Sponsor needs to address additional COVID-19 related risks to participants in the risk benefit section of the protocol.
11.13 Skin prick test	The mould allergen; Cladosporium herbarum is removed from SPT	The primary objective of this trial is to evaluate safety and tolerability during 28-days of treatment with HDM SLIT-tablet. From a clinical point of view the specific results of the SPT for moulds will have minimal, if any, impact on the overall trial results as well as data integrity and there is no effect on patient safety. The SPT panel will include Alternaria alternata , the most prevalent mould allergen

Flow chart

Trial period:	Screening	Treatment			Post-treatment	
		V2	TC	V3 ¹		
Visit ID:	V1					
Visit title:	Screening	Enrolment and administration of first tablet	Telephone contact	Final visit	Follow-up Telephone contact	Unscheduled Visit
Scheduled day:		Day 1	Day 8	Day 29 ⁴	Last day of treatment + 5-7 days	
Scheduling window:	Max 12 weeks prior to Day 1		+/- 1 day	+ 3 days		
Informed consent/assent	X					
Demography	X					
Smoking habits	X					
Medical history	X					
Previous ⁵ and concomitant medication	X	X	X	X	X	X
Height and weight	X	X				
Vital signs	X	X		X		(X)
FEV ₁ ⁶	X	X		X		(X)
Physical examination	X					(X)
Oropharyngeal examination		X ⁷		X		(X)
Assess symptoms of eosinophilic oesophagitis	X	X	X	X	X	(X)
Urine pregnancy test, if applicable ⁸	X	X		X		(X)
SPT ⁹	X	(X)				
Blood and urine sampling for safety analyses	X					(X)
Assess compliance with Inclusion/exclusion criteria	X	X				

¹ If a subject discontinues prior to completing the 28-day treatment period, the assessments of V3 should be performed 5-7 days after last IMP intake.

² Post-trial treatment with HDM SLIT-tablets must not be initiated before FU-TC has been performed.

³ Assessments at unscheduled visit(s) marked (X) are performed as applicable

⁴ Conducted on Day 29 in order to allow for diary completion for last day of treatment (Day 28)

⁵ Previous medication to be assessed only at V1 and covering at least 1 year.

⁶ Measure Forced expiratory volume in 1 second (FEV₁) and calculate the % of predicted FEV₁.

⁷ Oropharyngeal examinations will be done before IMP administration at V2.

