⁸ For female subjects of childbearing potential. Additional urine pregnancy tests should be performed during the trial, at an unscheduled visit, if a menstrual period is missed.

⁹ If medication that could interfere with the skin prick test has not been washed out at visit 1, the skin prick test must be performed after the interfering medication has been washed out and before tablet administration (See Table 5).

Trial period:	Screening	Treatment			Post-treatment	
Visit ID:	V1	V2	TC	V3 ¹	FU-TC ²	UV ³
Visit title:	Screening	Enrolment and administration of first tablet	Telephone contact	Final visit	Follow-up Telephone contact	Unscheduled Visit
Scheduled day:		Day 1	Day 8	Day 29 ⁴	Last day of treatment + 5-7 days	
Scheduling window:	Max 12 weeks prior to Day 1		+/- 1 day	+ 3 days		
Assess AEs since last visit/TC	X ¹⁰	X ¹¹	X	X	X ¹²	X
Provide the subject with a subject card	X					
Provide the Local and systemic allergic reaction emergency plan and instruct		X				
Dispense IMP and instruct in the use of IMP		X	(X) ¹³			(X) ¹⁴
Intake of IMP at clinic		X ¹⁴				
Provide and instruct in the use of the diary		X	(X) ¹⁵			(X) ¹⁵
Collect and evaluate diary.				X		
Collect IMP, perform compliance check and drug accountability ¹⁶				X		

¹⁰Any AE occurring during the visit from the time the informed consent/assent was signed

¹¹This includes AEs related to first IMP dose: Staff must record time of onset for any event occurring or worsening 0-30 minutes post dosing.

¹²If an AE was ongoing at the previous visit or if a new AE is identified at the telephone contact the subject could be asked to return to the trial site or have an additional telephone contact for follow-up.

¹³ Re-instruct in use of IMP, as applicable

¹⁴ For subjects with severe oral inflammation (e.g. oral lichen planus, mouth ulcers or thrush), oral wounds or following oral surgery, including dental extraction, or following tooth loss, initiation of IMP treatment should be postponed until the oral cavity has healed.

¹⁵ Re-instruct in use of the diary, as applicable

¹⁶ Collect unused, partly used and empty blister packages

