12 SAFETY

Information about AEs, whether reported by the subject, discovered by the investigator by reviewing diary records, detected through physical examination or other means, must be collected and recorded on the AE form and followed up as appropriate. Evaluation of AEs including severity, causality, outcome and seriousness assessments must be performed by a physician.

³¹ A tongue ulcer is a discrete, painful lesion affecting an area on the tongue, where the mucosa is eroded

Any AE occurring from the time the informed consent was signed by the subject and until the FU-TC must be recorded and reported on the AE page in the eCRF. This includes all AEs, even AEs occurring before the subject is administered the IMP and whether or not AEs are observed in connection with the trial assessments and conduct of the trial. TEAEs are defined as adverse events with start date on or after the time of first IMP administration and no later than 7 days after last IMP administration.

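### The TEAE definition looks only at start date, so an adverse event that begins in screening and worsens or becomes serious after the first dose can go uncounted

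*Combined protocol and SAP*

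**What the plan says.** The definition in section 15.8 covers "adverse events with start date on or after the time of first IMP administration", with the window closing 7 days after the last dose. Section 12 ("TEAEs are defined as adverse events with start date on or after the time of first IMP administration") and the Table of definitions carry the same rule. None of the three mentions worsening or a change in seriousness. Section 15.8 adds that "The evaluation of safety results will be based on TEAEs"; events that are not treatment-emergent are listed.

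Four other provisions decide which start date an event carries:

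- Section 12 collects adverse events from consent, including those before any dose. The flow chart sets the screening window at "Max 12 weeks prior to Day 1".
- Section 12.3: "One single AE form must be used per AE from start to resolution". A later paragraph, on recurrent events, calls for a new form if the event re-appears or its severity changes.
- Section 12.3.4: "The investigator must ensure that the worst-case severity and seriousness of an event is kept throughout the trial".
- Footnote 11 of the flow chart, repeated as a footnote to Table 2, says of the first dose: "Staff must record time of onset for any event occurring or worsening 0-30 minutes post dosing".

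Two provisions turn worsening into an adverse event directly. Section 12.1.1 does so for conditions recorded as medical history, and section 11.10 for oropharyngeal findings after the first dose.

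**The concern.** A single-arm safety trial has no control group to separate drug effect from background, so treatment-emergence is its main filter. Deterioration after the first dose is what that filter should keep. A definition based on start date alone keeps it only if the site opens a new record dated at the deterioration. The recording rules require that in some situations, are silent in one and can be read two ways in another.

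At stake is whether an event that became serious, or led to discontinuation, during treatment is counted under the matching endpoint in section 2.3 or 2.4. The answer could also differ between sites that read sections 12.3 and 12.3.4 differently. Any resulting error goes one way: the affected counts can only be too low.

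**Working it through.** **1. Tracing each kind of event through the rules.** Each row assumes a problem present before the first dose that changes afterwards.

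| Situation | Governing text | Post-dose record? | Counted as TEAE? |
|---|---|---|---|
| Medical-history condition, first worsens after dosing | 12.1.1 | Yes | Yes |
| Oropharyngeal finding before dosing, worse afterwards | 11.10 | Yes | Yes |
| Recurrent event, severity changes or event re-appears | 12.3, recurrent-event paragraph | Yes | Yes |
| Continuous screening event, severity increases | 12.3 one-form rule and 12.3.4, against the severity sentence in the recurrent-event paragraph | Unclear | Unclear |
| Medical-history condition that already became an adverse event in screening, worsens again after dosing | 12.1.1 against the one-form rule | Unclear | Unclear |
| Screening event becomes serious, severity unchanged | 12.3 one-form rule and 12.3.4; no new-form rule | No | No |
| Screening event leads to discontinuation after dosing, no new record | 12.3 one-form rule | No | No |

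The last row creates a visible mismatch. Section 5.1 requires an adverse event involved in a discontinuation to be recorded as the primary reason, so the subject appears under that reason in the disposition table (section 15.3). The same subject is absent from the endpoint of TEAE leading to discontinuation.

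Such events can be present at first dose. For asthmatic subjects with certain infections, section 9.2 postpones treatment until improvement, which is not the same as resolution.

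**2. How many subjects.** The documents give no rate, so these are assumptions. Suppose 20–40% of subjects have a screening event, 10–20% of those have it ongoing at visit 2, and 5–20% of those worsen:

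- low: 250 × 0.20 × 0.10 × 0.05 = 0.25 subjects
- high: 250 × 0.40 × 0.20 × 0.20 = 4 subjects

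This counts subjects with such an event. It is an upper bound on subjects lost from the primary endpoint, because many will have another TEAE.

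**3. Primary endpoint.** A subject is lost only if the worsened event is the sole candidate TEAE. Take a wider assumed share w of 1–5% with a worsened screening event, an assumed TEAE proportion r of 60–90%, and independence between the two. Subjects lost = 250 × w × (1 − r):

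- low: 250 × 0.01 × 0.10 = 0.25, or 0.1 percentage points
- high: 250 × 0.05 × 0.40 = 5, or 2.0 percentage points

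At the high end the result moves from 150/250 = 60.0% (exact 95% interval 53.6–66.1%) to 155/250 = 62.0% (55.7–68.0%).

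**4. Treatment-emergent SAE.** Here one event shows. With the exact 95% interval of section 15.8.1, 0/250 has an upper limit of 1.47%; 1/250 = 0.4% has an interval of 0.01–2.21%.

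**5. Section 15.1.** The plan's figure reproduces. The exact two-sided 90% upper limit for 1/500 is the 0.95 quantile of Beta(2, 499) = 0.945%, stated as 0.95%. For 2/500 it is 1.25%. Whether the definition could cause that step is taken up under the verdict.

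**The case against.** The best defence is that the plan already captures much of the worsening that matters. Asthma history is recorded under section 11.4, so in a subject with asthma a first worsening after dosing is an adverse event under section 12.1.1. The mouth and throat, the sites most relevant to this product, are covered by section 11.10. The worst-case rule does not say that severity is carried on the same form or that the earlier start date is retained. Footnote 11 asks for an onset time when an event worsens after the first dose, and section 12.3 enters visit 2 start times in the eCRF; a worsening recorded that way would meet the definition. Exclusion criterion E9 and the postponements in section 9.2 shrink the pool of events ongoing at first dose. Non-TEAEs are still listed, and serious events reach the sponsor within 24 hours, so no data are lost.

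Most of this stands. A reader might infer that every screening event that worsens drops out of the primary and all treatment-emergent endpoints; the documents do not support that. Nor do they support a downward bias in every treatment-emergent proportion. Solicited events come mainly from a diary started at first dose, and the endpoint of at least one IMP-related event is not labelled treatment-emergent, although section 15.8 leaves its handling open.

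Two things survive. No provision gives a new record when only seriousness changes, and for continuous events the one-form rule and the severity-change sentence point in different directions. Footnote 11 reaches only the 30 minutes after the first dose. A listing preserves the data but does not put the event into the endpoint.

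**Conclusion.** The point holds as a gap in the definition, made operative by the recording rules. It is clearest for treatment-emergent SAE and TEAE leading to discontinuation, where a single misclassified event would be visible. For the primary endpoint it is probably small: 0.1 to 2.0 percentage points under the assumed ranges, none of which comes from the documents. Section 3.2 expects more adverse event reporting than in earlier trials, which makes the lower part of that range more plausible.

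A reader might also infer that one missed event would carry section 15.1 from 0.945% to 1.25%, past the 1% it seeks to exclude. That does not follow. Section 15.1 concerns severe systemic allergic reactions and severe local swellings. To be missed, such an event would have to begin before any dose, still be present at visit 2 and then worsen. The anaphylaxis criteria in the Table of definitions describe onset within minutes to several hours, and the mouth and throat are examined before first dosing. Section 15.1 is also a sample-size rationale, and section 15.8 rules out hypothesis testing. The change is worth making because it is cheap and removes a one-directional error, not because the main result is in doubt.

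**What to change.** In the Table of definitions, section 12 and section 15.8, define a TEAE as an adverse event that starts, or that started earlier and worsens in severity or becomes serious, at or after the first IMP administration and within 7 days of the last.

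Reconcile sections 12.3 and 12.3.4 so that, for any event ongoing at first dose, an increase in severity or a change to serious gets its own dated record, whether the event is continuous or recurrent. State how the worst-case rule applies to the earlier and later records.

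State also how an event that began in screening and leads to discontinuation without a change in severity or seriousness is reported. It would still fall outside the revised definition, so the disposition table and the endpoint could still differ.

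The cost is protocol and analysis wording plus one eCRF completion instruction. A few more events will be counted, so reported rates become slightly less favourable.
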